#### 2.1.2 Secondary Objectives and Endpoints

Secondary objectives and endpoints will be assessed from time of start of USB002 or placebo infusion (Visit 1/Day 1) to Day 28.

Secondary endpoints include:

- All-cause mortality at Day 60.
- Number of ventilator-free days (defined as the number of days between Visit 1/Day 1 and Day 28 that subjects are both alive and free of mechanical ventilation [MV]; freedom from MV is further defined as free from MV for at least 48 hours after extubation).
  - In the case of repeated MV, duration of MV will be summed for the purposes of calculation. In the case of tracheostomy, the same criteria apply.
- Proportion of subjects weaned from mechanical ventilation through Day 28 (defined as free from MV for at least 48 hours after extubation. In the case of tracheostomy, the same criteria will apply). This applies only to subjects on mechanical ventilation at baseline.
- Proportion of subjects progressing from non-invasive (at baseline) to mechanical ventilation. This applies only to subjects not on mechanical ventilation at baseline.
- Time to progression (TTP) from non-invasive to mechanical ventilation.

- In the case of repeat admission to hospital and/or ICU within the first 28-days, the time from first treatment with study medication will be used to calculate TTP to MV;
- Number of days of vasoactive agent usage (defined as use of a vasoactive agent for 6 hours or more within any 24-hour period);
- Time (days) to hospital discharge;
- Changes in Ordinal Scale for Clinical Improvement (OSCI) status (see Appendix 1) from Visit 1/Day 1 to Day 28, defined as 1) time to change and 2) proportions of subjects, with 1-point and 2-point clinical status changes utilizing a time-to-event analysis from time of start of infusion (Visit 1/Day 1) of study medication to Day 28 for the time to change analysis between active and placebo groups.

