If a subject's treatment is terminated after the Visit 1/Day 1 infusion begins, for any reason, all attempts will be made to conduct all remaining study visits and assessments,

as applicable (See Tables 2 and 3). End of Treatment (Part 1 – Visit 5; Part 2 – Day 16) procedures may be conducted during the 24-hour observation period. Missed End of Treatment assessments due to disease progression or early discharge, will be considered deviations.

Respiratory evaluations will be determined by recovery landmarks of time to acceptable spontaneous breathing efforts (up to 30 minutes), termination for the need of oxygen (see Spontaneous Breathing Trial [SBT]: Appendix 2), and time to discontinuation of ventilatory assistance, if applicable. Clinical status will be evaluated using the OSCI and physical examination findings.

Follow-up for AEs with a start prior to Day 28 will be followed to resolution, stabilization, or to Day 60. Survival will be captured during the follow-up period through to Day 60, regardless of treatment or hospitalization status. AEs with a start date after Day 28 will not be captured. Any SAE that occurs at any time, through to Day 60, will be collected.

Participation will terminate for all subjects on Day 60 or at early termination due to death, consent withdrawal or lost to follow-up.

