The secondary efficacy outcomes that are binary, e.g., subjects weaned from mechanical ventilation within the 28-day, subjects progressing from non-invasive (at baseline) to mechanical ventilation, the proportions will be compared using Fisher's exact test. Death will be considered unfavorable outcome for these analyses, i.e. death prior to Day 28 will be considered as on mechanical ventilation. In addition, analysis of subjects weaned from mechanical ventilation will be conducted on those who were on mechanical ventilation at baseline, and analysis of subjects progressing from non-invasive to mechanical ventilation will be conducted on those who were not on mechanical ventilation at baseline. Time to hospital discharge will be analyzed using Kaplan-Meier method. Subjects who are not discharged by Day 28 or die will be censored at Day 28 for the analysis.

All other secondary outcomes will be presented descriptively.

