5.3. Missing Data

All missing data from CRF will not be imputed. Missing data will be considered missing at random.

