Achieving 1-point OSCI Decrease at Visit (Yes/No)	= Yes, if OSCI at visit – OSCI at Day 28 (or End of Treatment) ≥ 1 = No, OSCI at visit – OSCI at Day 28 (or End of Treatment) < 1 = null, if OSCI at Day 1 and/or at visit were missing	
Time to Achieving 1-point OSCI decreasing	= Date of first achieving 1-point OSCI decreasing – Study Day 1 + 1 = null if never achieving 1-point decreasing	

Outcome	Calculation	Comment
Achieving 2-point OSCI Decrease at Visit (Yes/No)	= Yes, if OSCI at visit – OSCI at Day 28 (or End of Treatment) ≥ 2 = No, OSCI at visit – OSCI at Day 28 (or End of Treatment) < 2 = null, if OSCI at Day 1 and/or at visit were missing	
Time to Achieving 2-point OSCI decreasing	= Date of first achieving 2-point OSCI decreasing – Study Day 1 + 1 = null if never achieving 2-point decreasing	

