8.3.6. Time to hospital discharge

Total days from Day 1 to hospital discharge will be listed and summarized.

8.3.7. Change of OSCI status from Day 1 to Day 28

For each subject, following outcomes will be calculated:

- Days from baseline to the date with OSCI score decreased 1-point from baseline
- Days from baseline to the date with OSCI score decreased 2-point from baseline
- OSCI score change from baseline to Day 28
- Achieving 1-point decrease of OSCI score at Day 28 (Yes/No)
- Achieving 2-point decrease of OSCI score at Day 28 (Yes/No)

These outcomes will be summarized.

All OSCI data will be listed.

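### The SAP has no rule scoring a death before Day 28 as OSCI 8, so such a death can drop out of the Day 28 OSCI summaries or even count as a responder

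*SAP*

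**What the plan says.** **Scale.** Protocol Appendix 1 defines the OSCI from 0 to 8, and 8 is death.

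**Flags.** SAP 7.2 derives the 1-point flag as "Yes, if OSCI at visit – OSCI at Day 28 (or End of Treatment) ≥ 1". The 2-point flag has the same form. Each flag is "null, if OSCI at Day 1 and/or at visit were missing". The time to a 1-point decrease is "null if never achieving 1-point decreasing".

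**Summaries.** SAP 8.3.7 summarizes the Day 28 flags, the times to a decrease, and the "OSCI score change from baseline to Day 28".

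**Missing data.** SAP 5.3 states "All missing data from CRF will not be imputed" and treats what is missing as missing at random.

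**End of participation.** Protocol 3 states "Participation will terminate for all subjects on Day 60 or at early termination due to death, consent withdrawal or lost to follow-up".

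**Death in other outcomes.** For binary secondary outcomes, Protocol 7.2.1 states "Death will be considered unfavorable outcome for these analyses". Its examples are ventilation outcomes, and the OSCI is not named. The SAP carries no such rule to the OSCI.

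**Direction.** Protocol 2.1.2 defines the endpoint through "proportions of subjects, with 1-point and 2-point clinical status changes". SAP 6.2 attributes decreases to the protocol, and the flags and times in SAP 7.2 and 8.3.7 follow that direction. What SAP 6.2 declares as changed is the loss of the time-to-event estimates, not the loss of one direction.

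**The concern.** On this scale a dead subject's state at Day 28 is known: it is the worst category. The SAP does not use that. Its general rules for missing scores apply instead, and they treat the absence of a Day 28 record as uninformative. An OSCI responder proportion or mean change restricted to subjects with a Day 28 record can then become a survivors-only figure, and a group with more deaths can look better on clinical status than a group with fewer.

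The End of Treatment alternative in the flag adds a second route to a wrong answer, because it may classify a subject on a score taken before the death. In groups this small, one subject visibly moves a percentage, and readers will take a descriptive table at face value when they look for an early efficacy signal.

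**Working it through.** The plan states no figure for this point, and no sample size, power or alpha depends on it. The check sets the rules side by side and then illustrates the size.

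**1. What happens to a death.** In Part 1, Protocol 5.4.2 schedules post-baseline OSCI at Visit 5, Day 16 and Day 28. Nothing is scheduled at death. Take a subject with baseline OSCI 5 and End of Treatment OSCI 3 who dies on Day 15. The documents allow three readings:

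| Reading | Calculation | 1- and 2-point flags |
|---|---|---|
| No Day 28 score recorded, null rule applied | none | null, out of the denominator |
| End of Treatment used as fallback | 5 − 3 = 2 | Yes and Yes |
| A score of 8 is entered for Day 28 | 5 − 8 = −3 | No and No |

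Nothing in the documents selects the third reading.

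**2. The flag formula.** As printed, it subtracts the Day 28 score from the visit score. At the Day 28 visit the two are the same number, the difference is 0, and every subject with a score is a No. SAP 8.3.7 defines the decrease from baseline, so baseline minus Day 28 is evidently meant. All figures below assume that correction.

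**3. Size of groups.** SAP 2 gives 6 + 6 + 6 + 3 = 21 subjects. Three complete cohorts at 3 active and 3 placebo give 9 per pooled arm. The split of the last 3 is not given, so each pooled arm has between 9 and 12 subjects.

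**4. Effect on the proportion.** Let n be the arm size, k the deaths without a Day 28 score, and x the improved survivors. With deaths null the proportion is x/(n − k). With deaths scored 8 it is x/n. The difference is xk/[n(n − k)]. The values of k and x are assumptions.

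| n | x | k | Deaths null | Deaths scored 8 | Difference (points) |
|---|---|---|---|---|---|
| 9 | 5 | 1 | 5/8 = 62.5% | 5/9 = 55.6% | 6.9 |
| 9 | 5 | 2 | 5/7 = 71.4% | 55.6% | 15.9 |
| 9 | 5 | 3 | 5/6 = 83.3% | 55.6% | 27.8 |
| 12 | 6 | 1 | 6/11 = 54.5% | 6/12 = 50.0% | 4.5 |
| 12 | 6 | 2 | 6/10 = 60.0% | 50.0% | 10.0 |
| 12 | 6 | 3 | 6/9 = 66.7% | 50.0% | 16.7 |

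Over n = 9 or 12, x = 3 to 6 and k = 1 to 3, the difference runs from 2.3 to 33.3 points.

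Under the fallback reading, an arm of 9 with 5 improved survivors and the one death from step 1 shows (5 + 1)/9 = 66.7%. The same arm can therefore be reported as 55.6%, 62.5% or 66.7%.

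**5. Ranking.** An arm of 9 with 4 improved and 3 deaths shows 4/6 = 66.7% with deaths null. That is ahead of an arm with 5/9 = 55.6% and no deaths. With deaths scored 8 the order reverses: 4/9 = 44.4% against 55.6%.

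**6. Change score.** This is a separate illustration with n = 9, all at baseline 5, survivors changing by −3 and each death by 8 − 5 = +3. With deaths null the mean is −3.0 for any k. With deaths scored 8 it is [(9 − k)(−3) + 3k]/9, which gives −2.3, −1.7 and −1.0 for k = 1, 2 and 3.

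**The case against.** The best defence is that no sentence in the SAP says deaths are null. The null rule applies only to a missing score. Protocol 7.1 has the worst OSCI recorded on each measurement day, and Protocol 5.3 collects OSCI assessments beyond the schedule, so a site could enter an 8. That subject would then be a No and stay in. SAP 7.2 also refers to programming specifications, outside the documents reviewed, for the complete derivations. This stands to the extent that a reader who infers that every death before Day 28 is excluded goes further than the text. It does not close the gap, because nothing requires an 8 to be entered or carried to Day 28.

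A reader might also infer that the SAP looks only at improvement. That is true of the flags and times but not of SAP 8.3.7 as a whole, which also summarizes the signed change to Day 28 and lists all OSCI data. Recorded worsening would show there, though a death with no score would not.

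Nor do the documents support the inference that deaths or deterioration are hidden. SAP 8.2.1 tabulates treatment-emergent events leading to death by dose cohort. SAP 8.3.1 lists deaths and, where data permit, gives the Day 60 rate. SAP 8.3.2 counts ventilator-free days only while alive. These displays limit the harm, but they do not correct the OSCI table.

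Finally, the null for time to a decrease applies to anyone who never improves, dead or alive, so it is not a rule that singles out deaths.

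**Conclusion.** The point holds as a gap in the derivation rules. If no Day 28 score of 8 is recorded, a death before Day 28 leaves the Day 28 responder proportions and the change score. If End of Treatment serves as a fallback, the same death can count as a responder. The printed flag formula is separately wrong at the Day 28 visit. The narrowing from changes to decreases in the flags and times is real and undeclared.

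The size is modest and uncertain. In the plainest illustration, 9 per arm with 5 improved and 1 death, it is 6.9 percentage points. It grows with more deaths and can reverse the order of the arms. Death and improvement counts are assumptions, since the documents give neither. The affected outcomes are secondary and descriptive, cover 21 subjects, and feed no test, because SAP 7.4 makes no inference. The change should be made before the tables are programmed, but it does not call the trial's safety reporting into question.

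**What to change.** In SAP 7.2 and 8.3.7:

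- Set OSCI to 8 from the date of death through Day 28 for every subject who dies on or before Day 28.
- Keep these subjects in the denominator as No for the 1- and 2-point flags, and include them in the change from baseline to Day 28.
- State that an End of Treatment score never overrides a death.
- Write the flag as baseline OSCI minus Day 28 OSCI, to agree with SAP 8.3.7.

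In SAP 6, declare that the protocol's 1- and 2-point changes were narrowed to decreases for the flags and times. Alternatively, also report 1- and 2-point increases at Day 28, with death as 8.

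The cost is a few lines in the SAP and the matching programming specifications. No new data are needed, because survival is already captured through Day 60. The downside is that reported improvement rates may be slightly less favourable.

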7.3. Interim Analysis

There are no formal interim analyses planned. Safety and tolerability review will be conducted by the DSMB.

7.4. Analysis Methods

All calculations and analyses will be performed using SAS version 9.4 or higher under the Windows Server 2012R2 operating system at McDougall Scientific Ltd. in Toronto, Canada. Continuous data will be summarized via PROC MEANS - mean, standard deviation, median, range, and 95% CIs, while categorical data will be presented as counts and percentages (or proportions) via PROC FREQ for the descriptive displays.

No statistical inference will be made for all outcomes.

8. Results

8.1. Study Subjects

All enrolled and treated subjects will be the analysis population for all analyses. All data collected in EDC will be at a minimum listed.

All outcomes will be summarized between the total treated subjects and total placebo subjects.

All safety and subject level outcomes will also be summarized by cohort (assigned dose level). All placebo groups will be combined as one group.

For all efficacy outcomes, see 8.2.1 and 8.2.2, the difference between treatment and placebo groups within each cohort (dose level) will also be presented, if data applicable.

All available data of screen failures will be provided in a separate listing.

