### **7.2.3 Safety Analyses**

All subjects who are enrolled and infusion dose of study drug/placebo was started will be included in the descriptive analysis. All safety and tolerability assessments will be based on the safety analysis set, which is defined as all subjects who have been randomized into the study. All subjects will be included in the analyses irrespective of protocol deviations or discontinuation from the study. No formal statistical analysis will be performed on safety data. Part 1 and Part 2 will be presented separately.

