Respiratory distress in untreated COVID-19 infected patients presents as a progressive continuum from SOB to cardiopulmonary collapse and death. It is diagnosed in symptomatic patients with bilateral lung infiltrates with confirmed positive tests for COVID-19. Without supportive therapy, pulmonary distress rapidly progresses to hospitalization where supplemental oxygen can be given by nasal cannula, high-flow mask, BiPAP mask, and eventually intubation and assisted ventilation. Overall, the physiological damage to cells and structures of the lung can begin within hours of exposure and progress within days (Fahy 2012). The pathologic hallmarks of COVID-19-induced pulmonary distress include neutrophilic alveolitis, hyaline membrane disease secondary to protein transudation and precipitation in the airspace, microthrombi secondary to the generation of procoagulant mediators as well as endothelial and epithelial injury. For these reasons, there is considerable interest in the use of an Angiotensin 1-7 [A(1-7)] to treat patients who have developed respiratory distress from COVID-19 infection (Soto 2020, Piero 2020, NCT 04332666).

This study's investigational product USB002 is pharmaceutically formulated A(1-7), a non-hypertensive derivative of Angiotensin-II (A-II) and is suspended in a vehicle as a sterile solution of USB002 (22.5 mg/ml) which is stable at room temperature for 90 days.

According to the protocol (see Section 4.1 Study Design), this clinical trial includes two parts (dose escalation phase and dose expansion phase). Due to enrolment difficulty to find subjects meeting the study eligibility criteria, in Dec. 2022, the sponsor decided to stop the enrollment and terminate the trial early, when 21 subjects (all Part 1) have been enrolled: 6 subjects in each of the first three cohorts (90, 300 and 600 ug/kg/day) and 3 subjects in Cohort 4, (900 ug/kg/day).

3. Objectives

The objectives of the study are twofold:

- To determine the safety and tolerability of USB002 in treatment of respiratory distress from COVID-19 infection; and
- To identify an early efficacy signal of USB002.

Part 1:

- To determine the maximum tolerated dose (MTD) of USB002 (up to 900 ug/kg/day).

Part 2:

- To determine preliminary efficacy of the USB002 MTD following up to 14 days of continuous infusion.

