3.2. Secondary Objective(s)

None

4. Study Design and Endpoints**4.1. Study Design**

This randomized, double-blinded, placebo-controlled study will be conducted in two parts:

Part 1 will escalate through four sequential doses of USB002 to determine the MTD. Part 2 will determine preliminary efficacy of the USB002 MTD dose identified in Part 1.

In Part 1 (dose escalation phase), the study will follow a traditional “3+3” design with three subjects in each cohort receiving SOC plus USB002 and three subjects in each cohort receiving SOC plus placebo. Cohorts will be enrolled sequentially for USB002 dose, with subjects receiving active drug at four sequential cohort doses of 90, 300, 600 and 900 ug/kg/day. The decision to dose-escalate, de-escalate, or increase the number of subjects in any dose level will be made by a Data Safety Monitoring Board (DSMB) based on the safety review of each cohort. Escalation will continue until Part 1 enrollment is completed and the MTD is determined.

In Part 2 (dose expansion phase), subjects will be randomized 1:1 to receive either SOC plus USB002 at the MTD established in Part 1 or SOC plus placebo infusion for up to 14-days. Infusion will be discontinued at any time if $\text{SpO}_2 \geq 94\%$ on room air. Visits will continue up to Day 28, if subject is still hospitalized. The Day 28 and Day 60 follow-up visits will be conducted by phone (Telemed) if discharged.

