7.1. Analysis Data Sets

7.1.1. Full Analysis Set (FAS)

Full Analysis Set is defined as all subjects who have received at least one dose of study medication. All safety and efficacy assessments will be analysed based on the analysis dataset.

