8.1.4. USB002 Administration

USB002 administration data, including dose of administration, infusion start/end date, start/end time, start rate of infusion, and all information of infusion rate changes, infusion incompletion reason, and related AEs, if applicable, will be listed.

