8.2.1. Adverse Events

Only treatment emergent adverse events (TEAEs) will be summarized. Summaries will be provided by dose level cohort with all placebo groups combined. Following summaries will be provided:

- Overview of TEAEs - include the total number of TEAEs, serious TEAEs, DLT, and TEAE leading to death
- TEAEs by MedDRA System Organ Class (SOC) and Preferred Term (PT)
- TEAEs by MedDRA SOC, PT, and severity
- TEAEs by MedDRA SOC, PT, and relationship to treatment
- TEAEs by MedDRA SOC, PT, and outcome
- Serious TEAEs by MedDRA SOC, and PT
- TEAE leading to death
- DLT.

All these summaries will include the counts and frequencies of events, and of subjects who had events.

All TEAEs will be listed by subject. Serious TEAEs, TEAEs leading to death, and DLTs will be listed separately.

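### SAP 8.1 tabulates safety by assigned dose level, with no rule for a subject who received a different dose or treatment

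*SAP*

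**What the plan says.** SAP 8.1 (Study Subjects) sets the grouping: "All safety and subject level outcomes will also be summarized by cohort (assigned dose level". SAP 8.2.1 applies it to adverse events: "Summaries will be provided by dose level cohort with all placebo groups combined".

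The analysis sets decide who is included, not which column a subject sits in. SAP 7.1.1: "Full Analysis Set is defined as all subjects who have received at least one dose of study medication", and "All safety and efficacy assessments will be analysed based on the analysis dataset". The per-protocol set in SAP 7.1.2 only removes subjects who withdrew before 48 hours of treatment. Protocol 7.2.3 describes the safety set as one "which is defined as all subjects who have been randomized into the study", while Protocol 7.2.1 requires at least one dose. None of these gives a received-dose rule.

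What was actually infused is recorded. SAP 8.1.4 lists the dose given, reasons for incomplete infusion and "all information of infusion rate changes". These data go into a listing only. The exposure summary in SAP 8.1.1 covers durations, although Protocol 7.2.2 also promises total exposure.

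**The concern.** Safety by dose is the trial's primary outcome (SAP 4.2 and 8.2). For adverse events, laboratory values, ECGs and dose-limiting toxicities, the relevant exposure is what entered the vein. A subject given something other than the assigned treatment or dose would still be tabulated under the assigned level. A toxicity, or a clean record, could then be credited to a dose that subject never had.

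The documents show ways this could happen without being noticed on site:

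- The pharmacy calculates the dose for each subject on IWRS instructions (Protocol 3 and 3.1.5).
- One fixed infusion rate serves all dose levels (Protocol 3.1.5), so a preparation error would not show at the pump.
- Active and placebo vials carry identical labels (Protocol 3.1.2), and the pharmacy is blinded (Protocol 7.4.1).

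The columns are very small and SAP 7.4 rules out inference, so the counts are the result. A single misplaced subject is visible in them.

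**Working it through.** **Inputs**

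- Design per cohort (SAP 4.1): "three subjects in each cohort receiving SOC plus USB002", plus three on placebo.
- Enrolment at termination (SAP 2): "6 subjects in each of the first three cohorts (90, 300 and 600 ug/kg/day) and 3 subjects in Cohort 4, (900 ug/kg/day".
- Allocation 1:1 (Protocol 3.3).
- Placebo pooled across cohorts (SAP 8.1 and 8.2.1).

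**1. Reproduce the stated counts.** Enrolled: 3 × 6 + 3 = 21, as SAP 2 states. Planned: 4 × 6 = 24. Maximum: 4 × 12 = 48. Both match Protocol 3.

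**2. Column sizes.** If the design split held, the 90, 300 and 600 ug/kg/day columns have 3 active subjects each. Cohort 4 had 3 subjects in both arms together, and the number active is not stated. Assuming a permuted block of 6, the chances of 0, 1, 2 or 3 active are 0.05, 0.45, 0.45 and 0.05. Assuming simple 1:1 randomization they are 0.125, 0.375, 0.375 and 0.125. One or two active is therefore the likely case (0.90 or 0.75). Pooled placebo is 3 × 3 = 9 plus 0 to 3 from Cohort 4, so 9 to 12.

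**3. Weight of one subject, 100/n points**

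| Column | n | One subject |
|---|---|---|
| 90, 300 or 600 ug/kg/day | 3 | 33.3 |
| 900 ug/kg/day, if 2 active | 2 | 50 |
| 900 ug/kg/day, if 1 active | 1 | 100 |
| Pooled placebo | 9 to 12 | 11.1 to 8.3 |

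**4. What changes when a subject is regrouped (columns of 3)**

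- The subject with the only event was assigned dose A but received dose B. By assignment: A 1/3, B 0/3. By receipt: A 0/2, B 1/4. A falls by 33.3 points and B rises by 25.
- The subject moved out of A had no event, but another subject in A did. A goes from 1/3 to 1/2, a change of 16.7 points.
- The subject with the only event was assigned placebo but received active drug. Placebo goes from 1/9 to 0/8, or from 1/12 to 0/11 (11.1 or 8.3 points). The active column goes from 0/3 to 1/4. This case assumes the placebo column is formed by assignment, which the SAP does not state.

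So 33 points is the maximum for a column of 3, not the typical change.

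**5. Precision.** Suppose one of three assigned to active received placebo and nobody had an event. The table shows 0/3 (exact 95% interval 0 to 70.8%), whereas the evidence at that dose is 0/2 (0 to 84.2%). For 1/3 the interval is 0.8% to 90.6%. These columns are imprecise under either grouping; regrouping corrects attribution, not precision.

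**6. If no error occurred.** Assigned and received dose agree for every subject, and every table is unchanged.

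**The case against.** The strongest reply is that this is a missing convention, not a wrong result. Neither document reports a misdosed subject. If there was one, the SAP lists all EDC data (8.1), the dose given (8.1.4) and each DLT, serious event and death (8.2.1). With 21 subjects a reader could trace a recorded discrepancy by hand. This stands, and it sets the weight of the point. It does not make the rule suitable, because the tables themselves would still not reflect the discrepancy.

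Several stronger readings are tempting, and the documents do not support them.

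- *A wrong kit could put a subject at the wrong dose level.* Protocol 3.1.2 describes a single vial strength, 22.5 mg/mL. A wrong kit could swap active and placebo. A wrong level would need a preparation or dose-instruction error. Sequential cohorts, with enrolment halted during each DSMB review (Protocol 3.2), make that less likely.
- *Escalation was decided on misattributed data.* The DSMB reviewed unblinded EDC data between cohorts (Protocol 3.2 and 6.6). The tables planned in this SAP were not the basis for those decisions.
- *The SAP groups everything by assignment.* The word assigned is attached only to the cohort level for safety and subject-level outcomes. The efficacy sentence in 8.1 refers to dose level without it, and the split between treated and placebo subjects is not defined as assigned or received.
- *Ignoring rate changes is itself a misgrouping.* A rate change alters how much a subject received, but usually not to another cohort's level. It calls for a stated rule and a flag, not a move between columns.

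It is also fair to say that a preparation error would often give a dose matching no cohort level, so any received-dose rule must cover that case.

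**Conclusion.** The point holds as a conditional one about the final report. SAP 8.1 groups safety by assigned level and nothing in either document overrides it. A preparation or dose-instruction error, or an active/placebo kit swap, could therefore place a subject's events under a dose or treatment not received.

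The size is up to 33 points at the three lower doses, 50 or 100 points at 900 ug/kg/day if 2 or 1 were active, and about 8 to 11 points in pooled placebo. These figures assume that the 3 + 3 split held in the first three cohorts. The placebo figure also assumes grouping by assignment.

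A reader should not infer that a dosing error took place or that any escalation decision was affected. If every subject received what was assigned, the change has no numerical effect. It is a free improvement.

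**What to change.** In SAP 8.1:

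1. For safety summaries, replace the assigned dose level with the treatment and dose level actually received. Say explicitly that this also governs the active/placebo split.
2. Keep assigned arm and dose for efficacy.
3. State before unblinding how a received dose that matches no cohort level is classified. One option is to keep the subject in the assigned cohort, flagged and footnoted. The same rule can cover doses altered by rate changes.
4. List every subject whose received treatment or dose differs from assignment, including a statement that there are none if that is so.

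The cost is a short revision of a signed SAP and one actual-treatment variable. Dose and rate data are already due to be listed under SAP 8.1.4. Confirming which kit was infused may need IWRS or pharmacy records, whose content the documents do not describe. Protocol 7.1 places SAP sign-off before database lock and unblinding, so the rule should be set by then. If that point has passed, the same section lets the change be justified in writing and presented in the study report.
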